H1a: PTSD will be associated with increased systemic levels of IL-1b, TNF- α and IL-6. H1b: WTC workers with asthma and PTSD will have an increased expression of sputum neutrophilia and IL-6 levels. H1c: Increased sputum neutrophilia and higher IL-6 levels will be associated with poorer disease control among WTC workers with asthma.

2. Examine the longitudinal association between PTSD and symptom perception in WTC workers with asthma

H2a: WTC rescue and recovery workers with PTSD will be more likely to over-perceive asthma symptoms in naturalistic settings compared to participants without PTSD. H2b: Associations between subjective (Asthma Control Questionnaire, use of rescue medications, and Asthma Quality of Life Questionnaire scores) and objective (forced expiratory volume in 1 second [FEV₁]) measures of asthma control will be weaker among WTC workers with PTSD than those without PTSD.

3. Assess the relationship between PTSD and adherence to asthma SMB (medication adherence, trigger avoidance, and inhaler technique) in WTC workers and identify the pathways linking them

H3a: PTSD is associated with lower adherence to SMB among WTC workers with asthma. H3b: Asthma (identity, timeline, and cause), medication beliefs (necessity and concerns about controller medications), and over-perception of symptoms will mediate, in part, the influence of PTSD on SMB.

4. Develop and pilot test an integrated intervention for asthma and PTSD by adapting the Relaxation Response Resiliency Program (3RP), a mind-body program, with counseling to promote asthma SMB, and education to correct over-perception of asthma symptoms

H4: The intervention will be acceptable to WTC workers, change beliefs about asthma, correct symptom over-perception, improve asthma medication adherence and quality of life and reduce symptoms of PTSD. We are currently seeking approval for the observational portion of the study only. We will request IRB approval for the interventional (pilot) phase at a later date, in advance of commencing the pilot.

2) Background

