Next, an overall unconditional model will be fitted to identify the growth trajectory across time. To that end, we will fit a growth function for anxiety sensitivity, symptom perception, illness beliefs, and asthma SMB using linear, quadratic, and unstructured models. Relative model fit will be evaluated based on the: χ^2 index ($>.05$), the comparative fit index ($>.97$), the root mean squared error of approximation (RMSEA $<.05$), and the weighted root mean square residual when using WLSMV (WRMR $<.90$). The most parsimonious model with the best fit will be retained. Finally, we will fit the full structural model, including the hypothesized relationships. For example, PTSD will be included as a predictor of asthma SMB. To address the possible mediational effects of anxiety sensitivity, symptom perception, illness and medication beliefs on the relationship between PTSD and asthma SMB, we will fit models to estimate both direct and indirect effects, first separately, and then combined. Lagged effects of the time-varying predictors, as well as the effects of the latent growth variables themselves (intercept, slope, and their random effects) will be evaluated as potential mediators; we will also be able to assess models of complete vs. partial mediation.¹²⁸ Relative fit, as well as estimates of effect size will be calculated, along with Sobel tests and Monte Carlo CIs to evaluate the mediational hypotheses.²³⁴

 Mount Sinai	Protocol Title:	Assessing Inflammatory and Behavioral Pathways Linking PTSD to Increased Asthma Morbidity in WTC Workers
	Principal Investigator Name/Contact Info:	[name], DrPH [contact]; [contact]
	Primary Contact Name/Contact Info	[name], MS [contact]; [contact]
	Date Revised:	07/25/16
	Study Number:	IF# 1896970; GCO# 16-0945

Integrating Biological and Behavioral Pathways: Finally, we will employ LGCM to characterize the interrelation and relative contribution of biological and behavioral pathways linking PTSD and asthma morbidity (Figure 1).

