Power Calculation: Power calculations for LGCM were based on published methods.²³⁵ Effect size in this approach is defined as a null and alternative hypothesis value of the RMSEA index, which we hypothesize to be 0.05 (adequate fit) and 0.03 (good exact fit), respectively. Power in SEM can be conceptualized as a function of sample size and the number of parameters to be estimated in the model, relative to the information provided in the overall variance-covariance matrix of the observed variables. The estimated power is based on a proposed sample size of 360 (assuming that 80% of total sample will be on controller medications) with an 80% follow-up rate, yielding estimated power >0.80 for an average effect of 0.10 with an alpha of 0.05. Overall, despite the challenges of estimating *a priori* power for SEM approaches, especially those involving growth models, we believe the proposed study will be adequately powered to address this aim.

We will request a separate IRB approval prior to the intervention phase of the study that is outlined in Aim 4.

Aim 4. Develop and pilot test an integrated intervention for asthma and PTSD by adapting the 3RP, with counseling to promote asthma SMB, and education to correct over-perception of symptoms: **Overview:** Based on the results of Aim 3, we will script messages aimed to counter beliefs linked to low adherence and to support those that promote better asthma SMB; these messages will be incorporated into specific sessions of the 3RP (Appendix D). If Aim 2 shows symptom over-perception in participants with PTSD, we will also integrate strategies to train individuals to more accurately perceive symptoms by providing feedback.⁸⁷ We will conduct a proof-of-concept pilot RCT in a subset of 60 WTC workers with asthma and PTSD who have completed their 12-month study visit to test the enhanced 3RP for PTSD and asthma. We are currently seeking approval for the observational portion of the study only. We will request IRB approval for the interventional (pilot) phase at a later date, in advance of commencing the pilot.

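### Aim 3 plans to compare complete with partial mediation but sets no criterion or bound for the direct PTSD effect, and the fit indices it names cannot show that this effect is absent

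*Combined protocol and SAP*

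**What the plan says.** Hypothesis H3b (section 1, Objectives) predicts that asthma beliefs, medication beliefs and over-perception of symptoms "will mediate, in part, the influence of PTSD on SMB".

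The analysis is in section h), Data Analyses, Aim 3, under Latent Growth Curve Modeling. It has three steps: a measurement model, an unconditional growth model, and the full structural model.

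- In the growth step, relative model fit is judged by a chi-square index above .05, a comparative fit index (CFI) above .97, RMSEA below .05 and a weighted root mean square residual (WRMR) below .90. That step closes with "The most parsimonious model with the best fit will be retained".
- In the structural step, PTSD is a predictor of SMB, and "we will fit models to estimate both direct and indirect effects, first separately, and then combined". The plan adds that "we will also be able to assess models of complete vs. partial mediation".
- For the mediation question the tools are: "Relative fit, as well as estimates of effect size will be calculated, along with Sobel tests and Monte Carlo CIs to evaluate the mediational hypotheses".

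The Aim 3 power paragraph defines effect size as RMSEA 0.05 (null) against 0.03 (alternative). It describes the sample in these words: "The estimated power is based on a proposed sample size of 360 (assuming that 80% of total sample will be on controller medications". After allowing for one in five participants being lost to follow-up, it reports its result as "yielding estimated power >0.80 for an average effect of 0.10 with an alpha of 0.05". The scale of the 0.10 and the model degrees of freedom are not given. Nor is any power for the direct path or for the contrast of complete with partial mediation.

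**The concern.** Complete mediation is a claim of absence: once the mediators are in the model, nothing of the PTSD effect on SMB remains. Such a claim needs an upper bound on what remains. The plan gives no bound, no margin and no criterion.

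Of the tools listed, the Sobel test concerns the indirect effect. The Monte Carlo intervals are named alongside it, and no interval for the direct effect is specified. Relative fit is the tool that sets a model with the direct path against one without it. The only definition of relative fit in this section is the set of global cut-offs from the growth step. Those indices average misfit over the whole model, so one omitted path can be real and still leave them almost unchanged.

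At stake is how Aim 3 is interpreted. A report could say that beliefs, anxiety sensitivity and symptom perception carry the entire PTSD effect when the data are compatible with a direct effect of some size.

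**Working it through.** **Inputs.** Cohort of 400 (section c). The power paragraph's 360, described there as 80% of the sample, is 360/400 = 90%; 80% of 400 is 320. With 80% follow-up these become 360 × 0.8 = 288 and 320 × 0.8 = 256. Since the documents do not settle which applies, all four are carried. Alpha is 0.05. Assumptions of this check: two-sided tests; standardised effects; model degrees of freedom (df) of 50 and 100; and a maximum-likelihood discrepancy, although the plan specifies the WLSMV estimator.

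**1. The plan's own figure.** The noncentrality is (N−1) × df × RMSEA². The null of 0.05 is rejected when chi-square falls below the 5th percentile of its null distribution, and power is taken at RMSEA 0.03.

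| N | Power, df 50 | Power, df 100 | Smallest df for 0.80 |
|---|---|---|---|
| 360 | 0.61 | 0.87 | 83 |
| 320 | 0.54 | 0.81 | 99 |
| 288 | 0.49 | 0.75 | 116 |
| 256 | 0.43 | 0.68 | 139 |

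The stated power above 0.80 is attainable for a large model but cannot be confirmed without the df. It concerns overall fit and says nothing about a single path.

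**2. Can global fit reveal an omitted direct path?** Suppose the true standardised direct effect is 0.20 and the fitted model leaves it out.

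- Misfit: F0 = −ln(1 − 0.20²) = 0.0408.
- Noncentrality: (N−1) × F0, which is 255 × 0.0408 = 10.41 at N=256 and 359 × 0.0408 = 14.66 at N=360.
- RMSEA is below .05 when chi-square is below df × (1 + 0.0025 × (N−1)). At N=256 that is 81.88 (df 50) or 163.75 (df 100).
- Chi-square p is above .05 when chi-square is below 67.50 (df 50) or 124.34 (df 100).

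| N | df | P(RMSEA < .05) | P(chi-square p > .05) |
|---|---|---|---|
| 256 | 50 | 0.955 | 0.738 |
| 256 | 100 | 0.999 | 0.818 |
| 360 | 50 | 0.985 | 0.612 |
| 360 | 100 | >0.999 | 0.736 |

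The chi-square criterion is the stricter of the two, so the last column is also the chance of meeting both. CFI and WRMR were not computed, because they need model details that the documents do not give.

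**3. Can a test of the direct path reveal it?** For a standardised effect of 0.10, the noncentrality on the z scale is 0.10 × √(N × (1−R²x)/(1−R²y)). R²x is the share of PTSD variance explained by the other predictors, and R²y the share of outcome variance explained. With both at zero:

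| N | z-scale noncentrality | Power | Missed |
|---|---|---|---|
| 360 | 1.897 | 0.475 | 53% |
| 320 | 1.789 | 0.432 | 57% |
| 288 | 1.697 | 0.396 | 60% |
| 256 | 1.600 | 0.360 | 64% |

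About 783 participants would be needed for 80% power.

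Sensitivity at N=288: power is 0.22 with R²x=0.5 and R²y=0, 0.53 with R²x=0 and R²y=0.3, and 0.67 with R²x=0 and R²y=0.5. One-sided power is 0.60 (N=360), 0.52 (288) and 0.48 (256). If the 0.10 were Cohen's f², power would exceed 0.99.

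**4. Does the Sobel test help?** In a simulated one-mediator model with both mediator paths at 0.3 and a direct effect of 0.10, the direct path was missed in 52% (N=360), 60% (288) and 64% (256) of studies. The Sobel test was significant in nearly all of those. A clear indirect effect together with a non-significant direct one is therefore a common result even when mediation is only partial.

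**5. Precision.** The approximate 95% half-width for the direct effect, with R²x=0, is 1.96 × √((1−R²y)/N). With R²y=0 it is 0.122 (N=256) to 0.103 (N=360); with R²y=0.3 it is 0.102 to 0.086.

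**The case against.** The strongest reply is that the plan never says it will declare mediation complete. A reader might infer a rule that mediation is complete whenever dropping the direct path does not significantly worsen fit. No such rule is written. The parsimony sentence does not supply it either, because it closes the choice of growth function before the structural model is fitted. This stands, and the point here is the missing criterion.

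Relative fit could also mean a one-df comparison of nested models. By the formula in step 3 with both R² at zero, that comparison would find an effect of 0.20 with power of about 0.89 at N=256 (noncentrality 0.20 × √256 = 3.2). The step 2 figures therefore apply to the cut-offs that the section defines, and step 3 applies to the nested reading. Neither reading bounds the direct effect.

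A reader might take 0.10 as the plan's own direct effect and say that most studies would miss it. The documents call it an average effect on an unstated scale. The majority is also narrow at N=360 and reverses with a one-sided test or substantial explained outcome variance. Nor do the documents support saying that a margin of 0.10 could never be met, since step 5 shows half-widths below 0.10 under some assumptions.

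Two further inferences fail. Comparing the two models does not conflict with H3b, because it is one way to examine a prediction of partial mediation. And a remaining PTSD effect would not be overlooked in Aim 4: under Integrating Asthma SMB into 3RP, content follows the beliefs most strongly associated with SMB, and the adapted programme addresses PTSD itself.

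Much of the remedy is already planned, since both effects are to be estimated. Figure 5, the mediation model, is not visible in the text reviewed and may fix the df.

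**Conclusion.** The point holds in a limited form. Aim 3 sets out to contrast complete with partial mediation without a criterion, a bound on the direct effect, or power for that contrast. Judged by the global cut-offs the section defines, a model wrongly omitting a standardised direct effect of 0.20 would usually look acceptable: RMSEA passes in at least 95% of studies and chi-square in 61% to 82%, across N of 256 to 360 and df of 50 to 100. Judged by a significance test, a standardised 0.10 is missed in 53% to 64% of studies when little outcome variance is explained, and less often when much is.

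These figures rest on the assumed df, the maximum-likelihood approximation and a standardised scale that the documents do not confirm. The core conclusion does not depend on them: neither acceptable fit nor a non-significant path shows that an effect is absent. The change is worth making, because it replaces a fit-based contrast with an interval estimate.

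**What to change.** In Aim 3, Latent Growth Curve Modeling:

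- Keep the direct path from PTSD to SMB in the final structural model, whatever the fit comparison shows.
- Report the direct and indirect effects, each with a 95% confidence interval.
- State that acceptable or similar fit, or a non-significant direct effect, will not be reported as complete mediation.
- If the term is kept, use it only when the confidence interval for the direct effect lies within a margin fixed before the analysis, with its scale stated.

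In the Aim 3 power paragraph, state the model df and the scale of the 0.10, and reconcile 360 with 80% of 400.

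The cost is wording only, with no new data or visits, because both effects are already to be estimated. The downside is that a complete-mediation claim, which H3b does not predict, is given up unless the interval supports it.

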Potential participants with a diagnosis of asthma will be identified from the WTCHP database and our prior WTC cohort study (HSM#12-00422; consent included language authorizing contact for future studies). The research team will send out a letter from the study's PI, [name], or an investigator who is a practicing physician at the WTCHP sites. Participants will have 1 week to respond to the letter. If the research team does not hear back from the participant after 1 week, then we will call the participant to offer participation in the study. WTC workers who agree to

 Mount Sinai	Protocol Title:	Assessing Inflammatory and Behavioral Pathways Linking PTSD to Increased Asthma Morbidity in WTC Workers
	Principal Investigator Name/Contact Info:	[name], DrPH [contact]; [contact]
	Primary Contact Name/Contact Info	[name], MS [contact]; [contact]
	Date Revised:	07/25/16
	Study Number:	IF# 1896970; GCO# 16-0945

participate will be contacted by a research assistant (RA) who will explain the study and schedule an in-person assessment.

b) Inclusion and Exclusion Criteria

Inclusion Criteria: Participants will be ≥ 18 years of age, have a diagnosis of asthma made by a health care provider, and speak English or Spanish. Exclusion Criteria: WTC workers will be excluded if they have chronic obstructive lung disease (COPD) or other chronic respiratory illness. Additionally, individuals with a history of heavy smoking (≥ 15 pack-years) will be excluded because of the possibility of undiagnosed COPD. Current smokers will be included in the study if their cumulative smoking history does not exceed this threshold.

c) Number of Subjects

A total of 400 patients will be enrolled over a 3-year period and followed for 1 year. At the ISMMS site, we will recruit 300 patients. At the Queens College site we will recruit 100 patients.

d) Study Timelines

The study will take place from September 1, 2016 to August 31, 2021. Participants will be followed for 12 months with in-person interviews at baseline, 1 month, 6 months and 12 months.

Table 5. Study Timeline

TASK	Yr 1	Yr 2	Yr 3	Yr 4	Yr 5
Study Preparation	■				
Baseline interviews		■	■	■	
Follow-up interviews		■	■	■	
Data Analysis		■	■	■	
Pilot RCT				■	
Dissemination			■	■	■

e) Study Endpoints

N/A

f) Procedures Involved in the Human Research

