Power Calculations: We estimated rates of over-perception and asthma morbidity from our prior studies or the literature.^{27,109,154,155,168,229} We adjusted the sample size for the expected correlation of measurements within a participant (interclass correlation coefficient ≥ 0.8).²³⁰ These analyses showed that with 400 patients, the study will have $>90\%$ power to detect a 10% increase in the probability of over-perception in participants with PTSD. We also evaluated the power to identify whether the regression coefficients for the association between the ACQ/AQLQ scores and FEV₁ is different for patients with vs. without PTSD (equivalent to testing an interaction). These analyses showed that with 400 subjects (and 80% retention), the study will have an 82% power to detect a difference of 1 unit between the slopes of patients with and without PTSD.

Aim 3. Assess the relationship between PTSD and adherence to asthma SMB in WTC workers and identify the pathways linking them: Medication adherence analyses will be restricted to patients prescribed controller medications ($>80\%$ of the sample based on prior studies). Primary analyses will use electronic adherence measures; secondary analyses will use MARS scores and other SMB. The univariate association of adherence and PTSD will be assessed using a chi-square test. Multivariable analyses will use a GEE model (logit link function) to control for potential confounders as listed above. We will use similar approaches to assess the associations of potential mediators (over-perception of symptoms, anxiety sensitivity, and illness and medication beliefs, Figure 5) of the relationship between PTSD and medication adherence.

 Mount Sinai	Protocol Title:	Assessing Inflammatory and Behavioral Pathways Linking PTSD to Increased Asthma Morbidity in WTC Workers
	Principal Investigator Name/Contact Info:	[name], DrPH [contact]; [contact]
	Primary Contact Name/Contact Info	[name], MS [contact]; [contact]
	Date Revised:	07/25/16
	Study Number:	IF# 1896970; GCO# 16-0945

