Latent Growth Curve Modeling (LGCM): We will employ LGCM approaches to test the mediation model presented in Figure 5.^{231,232} The analysis will involve longitudinal assessment of asthma SMB across 3 time points (0, 6, and 12 months). We hypothesize that both time-varying covariates (e.g., illness and medication beliefs) and time-invariant covariates (e.g., age, sex, etc.) will predict asthma SMB assessed at these time points. We also hypothesize potential lagged effects of covariates at earlier time points. As a first step, we will identify the measurement model for the latent variables using confirmatory factor analysis. Specifically, we will create latent variables representing random effects intercepts and slopes for illness and medication beliefs (IB_{t0} , IB_{t6} , and IB_{t12} ; where $t0$ represents baseline illness beliefs scores), anxiety sensitivity and asthma SMB measures. Illness representations will be measured by 5 independent factors (i.e., identity, timeline, etc.), medication representations by 2 factors (i.e., necessity and concerns), and anxiety sensitivity by 3 factors. Emotional representations will be modeled as a single domain. This approach will allow us to test specific pathways. This model will also include the control variables listed above. We will estimate slope and intercept parameters using a Weighted Least Squares Mean-Variance adjusted (WLSMV) estimator, which provides robust estimates for complex models with modest sample sizes. We will test this measurement model for absolute fit using Chi-square and RMSEA statistics.^{232,233}

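### The Aim 3 growth-model power rests on N=360, described as 80% of the sample, but 80% of the 400 enrolled is 320; the stated power is uncheckable from the text, not shown false

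*Combined protocol and SAP*

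**What the plan says.** All references are to the Combined protocol and SAP.

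- Section c) Number of Subjects: "A total of 400 patients will be enrolled over a 3-year period and followed for 1 year". The same total of 400 appears under Resources, under Recruitment Methods and in the Aim 2 power calculation.
- Data Analyses, Aim 3: "Medication adherence analyses will be restricted to patients prescribed controller medications", a group put at more than 80% of the sample on the basis of prior studies.
- Aim 3, Power Calculation, on the sample: "The estimated power is based on a proposed sample size of 360 (assuming that 80% of total sample will be on controller medications"). Four in five of these are assumed to be retained.
- Same paragraph, on the method: "Effect size in this approach is defined as a null and alternative hypothesis value of the RMSEA index", set at 0.05 (null) and 0.03 (alternative). It adds that power depends on the number of parameters, but gives no count.
- Same paragraph, on the result claimed: "yielding estimated power >0.80 for an average effect of 0.10 with an alpha of 0.05".
- Latent Growth Curve Modeling: "Illness representations will be measured by 5 independent factors", with further factors for medication beliefs, anxiety sensitivity and emotional representations. Direct and indirect effects are fitted first separately and then together, "along with Sobel tests and Monte Carlo CIs to evaluate the mediational hypotheses".

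**The concern.** The sample size behind the power statement does not follow from the percentage offered to explain it. A reader who trusts the 80% gets 320, and one who trusts the 360 must infer a controller share of 90% that the paragraph does not state.

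Two features make the effect of this hard to judge. RMSEA power depends on the model's degrees of freedom, which the text omits. The paragraph also switches from an RMSEA contrast to an average effect of 0.10 without saying what that number measures. H3b is a mediation hypothesis, and the plan concludes that it is adequately powered for this aim.

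Aim 4 builds its intervention messages on the beliefs that Aim 3 links to self-management. A null mediation result would be hard to interpret if the power for it is unknown.

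**Working it through.** **Sample size.** Inputs are 400 enrolled (Number of Subjects), and 80% on controllers and 80% follow-up (Aim 3 Power Calculation).

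- 400 × 0.80 = 320; 320 × 0.80 = 256.
- The plan's 360 is not reproduced: 360/400 = 0.90, and 360/0.80 = 450, a total stated nowhere. If 360 is meant to be the number after follow-up, 360/(0.8 × 0.8) = 562.5 would have to be enrolled.
- 360 × 0.80 = 288. Ratios: 360/320 = 288/256 = 1.125, an excess of 12.5%.

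**RMSEA power.** The noncentrality is λ = (N − 1) × df × RMSEA². The critical value is the 5th percentile of the noncentral chi-square at RMSEA 0.05. Power is the probability of falling below it at RMSEA 0.03. The plan's figure above 0.80 can be neither reproduced nor refuted, because df is missing.

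| N | Minimum df for 0.80 | Power at df 50 | df 100 | df 150 |
|---|---|---|---|---|
| 360 | 83 | 0.61 | 0.87 | 0.96 |
| 320 | 99 | 0.54 | 0.81 | 0.93 |
| 288 | 116 | 0.49 | 0.75 | 0.89 |
| 256 | 139 | 0.43 | 0.68 | 0.83 |

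Models with df of about 83 to 138 reach 0.80 at 360 but not at 256. Like for like, the band is 83 to 98 for 360 against 320, and 116 to 138 for 288 against 256.

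To see where planned models might lie, assume one score per construct, three waves and linear growth. With k constructs, df = [3k + 3k(3k+1)/2] − [2k + 2k(2k+1)/2 + 3k].

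- k = 2: df 7, power below 0.20 at every N.
- k = 6: df 81, just under 0.80 at 360.
- k = 7: df 112, power 0.90 at 360 and 0.72 at 256.
- k = 13 (5 illness, 2 medication, 3 anxiety sensitivity, 1 emotional, symptom perception, self-management): df 403, power 0.996 at 256 and higher at the other Ns.

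**The effect of 0.10.** Three readings, two-sided 0.05:

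- One standardised path, Fisher z: power = Φ(atanh(0.10) × √(N − 3) − 1.96) = 0.47, 0.43, 0.40 and 0.36 at N = 360, 320, 288 and 256.
- Cohen's f² of 0.10, one tested predictor: above 0.99 at all four Ns.
- An indirect effect a × b of 0.10 (single mediator, standardised, no direct effect). Sobel z = ab/√(a²s_b² + b²s_a²), with s_a² = (1 − a²)/(N − 2) and s_b² = (1 − b²)/[(N − 3)(1 − a²)], evaluated by simulation. At N=256: 0.997 for 0.316 × 0.316, 0.89 for 0.2 × 0.5, and between 0.67 and 0.68 for 0.15 × 0.67. The last pair gives about 0.82 at 360 and 0.77 at 320.

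**Detectable indirect effect.** On the same single-mediator assumptions with equal paths, 80% power at N=256 needs about 0.225 per path for Sobel and about 0.20 for a joint-significance test. At 0.20 per path and N=256, Sobel power is only about 0.63. At N=320 the corresponding values are about 0.20 and 0.18.

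**The case against.** The best defence is that prior studies put the controller share above 80%, so 90% and hence 360 is possible. That stands as a possibility, but the power paragraph itself says 80%, and the two must agree.

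Three stronger readings are tempting, and the documents support none of them.

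- A reader might infer that the power claim is false. It is not shown to be: a large joint model keeps RMSEA power well above 0.80 at every N considered. Figure 5, which depicts the mediation model, is not shown in the text available here and may allow a parameter count.
- A reader might infer that the stated power concerns model fit only. The RMSEA contrast does, but the 0.10 could be an indirect effect, and power for that can exceed 0.80 even at 256. The metric is unclear, so it cannot be settled either way.
- A reader might take 256 as the corrected N. It counts complete follow-up only. The plan does not restrict the growth model to completers, and the controller restriction is worded for medication adherence alone, so other self-management behaviours start from 400.

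The plan also admits that prior power for such models is difficult to estimate. That is fair, but it does not explain the 360.

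**Conclusion.** The sample-size statement is wrong as written. The N is 12.5% above what the plan's own 80% of 400 gives: 360 against 320, or 288 against 256 with complete follow-up. This should be fixed, but it does not show that the study is underpowered.

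Under the RMSEA method, the discrepancy changes whether 0.80 is reached only for models of intermediate size, with df of about 83 to 138 at the widest. Very small models miss 0.80 at all four Ns and very large ones reach it at all four. The RMSEA contrast does not by itself give power for the H3b mediation tests. The undefined 0.10 does not fill that gap, because its power runs from 0.36 to above 0.99 depending on the reading.

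The arithmetic on N needs no assumption. The df thresholds assume a one-tailed 0.05 test of close fit, the construct counts assume the simplified growth model above, and the indirect-effect figures assume a single mediator with standardised paths, no direct effect and no covariates.

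**What to change.** In the Aim 3 Power Calculation:

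1. Reconcile the percentage and the N. Either use 320 (256 for complete follow-up), or state and justify 90% on controllers, giving 360 and 288.
2. Say that this N applies to the medication-adherence analyses, that other self-management behaviours start from 400, and whether participants with partial follow-up stay in the growth model.
3. Restate the RMSEA power at that N, with the df of the model it refers to.
4. Define the metric of the 0.10 effect.
5. Report the detectable indirect effect for H3b under the tests the plan names, with its assumptions. As a guide, for equal standardised paths, a single mediator and N=256, this is about 0.225 per path for Sobel; the 0.20 from a joint-significance test should not stand in for it.

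The cost is revised text and a power recalculation, with no new patients or visits. The only downside is that the restated figure may be slightly less favourable.
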